Management of Uncontrolled Hypertension (HTN)

NCT02922023

10/26/2022

Protocol

1. Title:

Management of Uncontrolled Hypertension: Ambulatory Blood Pressure Monitoring and Subsequent Modification of Therapy or Shifting Anti-hypertensive Medication to Night-time Dosing

2. Investigators:

Principal Investigator:

[name] [name].
Clinical Assistant Professor
Department of Pharmacotherapy and Translational Research

Sub-Investigators:

[name]
[name].
UF College of Pharmacy

[name].
Internal Medicine Physician
UF Health Internal Medicine – Medical Plaza

3. Abstract:

Ambulatory Blood Pressure Monitoring (ABPM) and its role in clinical practice continues to evolve. ABPM allows providers to obtain blood pressure readings over a 24hour period, to assess blood pressure at night to determine “dipping” status, and to evaluate the efficacy of anti-hypertensive therapy. By utilizing ABPM in uncontrolled hypertension patients in clinical practice, modifications in drug therapy can be based on a more comprehensive and accurate depiction of the patient’s overall blood pressure control throughout the day. Although, theoretically, an assessment of the 24-hour blood pressure of a patient prior to adjusting drug therapy should yield better blood pressure control, we would like to carry out a pilot study to investigate whether the modifications in therapy based on ABPM and the resulting impact on blood pressure control would be substantially different from simply switching the dosing of medication to night-time.

In this study, we will compare chronotherapy to ABPM. Data collected will include hypertension drug therapy regimen prior to and during the study, timing of medication administration, and dose, along with the patient’s office blood pressure values prior to study and one month after modification in therapy. This will enable us to explore

whether it is a practical endeavor to implement ABPM as a routine process for all uncontrolled hypertension patients or whether ABPM does not seem to provide considerable value over shifting the timing of drug administration.

4. Background:

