ABPM is primarily used to diagnose white coat hypertension, however, ABPM may be used to assess efficacy of blood pressure treatment by evaluating the patient's blood pressure control over a 24-hour period.⁵ The capability to provide night-time readings during sleep sets it apart from office blood pressure readings and home blood pressure readings, and it provides information for the determination of dipping status. Non-dipping status has been associated with target organ damage including left ventricular hypertrophy, microalbuminuria, cerebrovascular disease, congestive heart failure, vascular dementia, stroke, and myocardial infarction.⁶ The frequency of non-dipper patterns tends to be higher in hypertension that is secondary to specific medical conditions such as chronic renal failure, diabetes, and autonomic nervous system dysfunction than in uncomplicated primary hypertension. A study also showed that the percentage of patients that ingest all their antihypertensive medications in the morning was significantly greater in non-dippers than the dippers suggesting that non-dipping among treated patients is partly due to lack of 24-hour therapeutic coverage when administered in the morning.⁹

stages hypertension as Stage 1 with pressure. Adults between the ages of 18 and 59 years old or any adult with diabetes or chronic kidney disease are considered hypertensive with three consecutive blood pressure readings above 140/90 mmHg.⁷ Resistant hypertension is defined as blood pressure that remains above the goal of 130/80 mmHg despite the use of three anti-hypertensive agents at optimal doses including a diuretic, if possible, or blood pressure that is controlled with the use of four or more antihypertensive drugs.⁸ Although non-adherence is a common contributing factor to pseudo-resistant hypertension, it remains difficult to apply a simple, inexpensive, and reliable method in the clinical setting to quantify this factor when investigating potential causes for resistant hypertension.⁸ Additionally, seemingly resistant hypertension may be related to inadequate night-time blood pressure control leading to elevated blood pressures during sleep as well as a higher-than-normal morning rise/spike upon awakening.⁶

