move a medication to bedtime dosing, without relying on ABPM. Given that the initial cost associated with purchasing ABPM equipment (\$2500-\$5000) and software (\$2000-\$3000)¹¹ is not inconsequential, we propose this pilot study to determine whether ABPM in clinical practice is an investment that results in significant difference in blood pressure control when compared with chronotherapy.

5. Specific Aim:

We propose to conduct a pilot study to determine whether the incorporation of Ambulatory Blood Pressure Monitoring (ABPM) as routine procedure in clinic for uncontrolled hypertension influences how anti-hypertensive drug therapy is modified or if simply shifting the dosing of anti-hypertensive medications to night time achieves similar results. We will enroll 20 participants with uncontrolled hypertension, who are prescribed 3 anti-hypertensive medications. All twenty patients will undergo 24-hour blood pressure monitoring with ABPM at baseline and one month after change in therapy has been initiated; ten of the patients will be randomized to receive a shift in dosing schedule of anti-hypertensive medication to night-time without utilizing their ABPM results while the remaining ten will receive modifications in therapy based on their ABPM results and dipping status. The results of this study will assist in assessing the feasibility and benefits of the incorporation of ABPM into the routine management of hypertension.

6. Research Plan:

Patient eligibility

Inclusion criteria

1. Age \geq 18 years
2. Blood pressure of $>130/80$ mmHg
3. Currently receiving 3 anti-hypertensive agents, one of which is a diuretic, for at least six weeks

Exclusion criteria

1. Vulnerable populations
 - a. Pregnant women
 - b. Prisoners
 - c. Cognitively impaired persons
 - d. Economically and/or educationally disadvantaged
 - e. Human fetuses and neonates
 - f. Patients who work night-shift
 - g. Children
 - h. Conditions with visual field deterioration (Anterior Ischemic Optic Neuropathy, Glaucoma, Optic Nerve Disorders)

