
Follow-up will occur for both treatment groups after one month of initiating their modified anti-hypertensive regimen to see how changes in drug therapy impact their blood pressure control. Patients will arrange for their follow-up 24-hour ABPM screening. The procedure from the first ABPM screening will be repeated, and the patient will return the following day to remove the monitor, return their ABPM diary, and submit their ABPM results for analysis.

[figure not shown]

Chart 1: Flow chart demonstrating process for conducting the study

Aside from patients receiving ABPM, all patients will receive standard care in managing their hypertension involving hypertension follow-up appointments and adjustments in therapy to achieve adequate blood pressure control. For those patients who are in the group whose changes in therapy will be determined after evaluating their ABPM results, patients found to be dippers and would not benefit from the switch in dosing to nighttime will receive changes in therapy as would be expected in clinic as standard care if a dose increase/medication change is warranted. Clinical data will be obtained from standard blood pressure monitoring equipment provided by the clinic. Therefore, this study will not result in additional charges associated with the treatment and care of the patient.

Data collection will include age, sex, race, height, weight, comorbidities (Diabetes Mellitus, hyperlipidemia, history of stroke, transient ischemic attack, myocardial infarction, etc.), antihypertensive therapies including dosing schedule at baseline as well as after modification from receiving either treatment option, complete medication history including over-the-counter and herbal medications, whether or not the patient uses a home blood pressure monitor (yes or no), lifestyle history including caffeine and alcohol intake and tobacco use, number of years since HTN diagnosis, whether or not patient was at blood pressure goal at the follow-up visit at one month after initiating change in therapy (yes or no), and the blood pressure readings from the ambulatory blood pressure monitor at baseline and one month post initiation of change in drug therapy. Data will be obtained through EPIC, including the patient-recorded data such as the diary of activity during the 24 hours wearing the ABPM which will be scanned into EPIC. The results of the ABPM will be obtained from the ABPM software and may be scanned into EPIC for ease of access.

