Descriptive statistics, including REDCap (Research Electronic Data Capture) will be used to analyze patient data. Unique patient codes will randomly be assigned to each patient participating in the study through REDCap, and the patient code will serve as the identity of the patient throughout the study. The master list linking the patient codes to the specific patient names will be kept as a physical copy that will remain in a locked filing cabinet in HPNP Room 3313, and only the investigators will have access. The list will be shredded at the conclusion of the study. All electronic files containing clinical information will have PHI removed, and data will be stored on encrypted, password protected files accessed on a UF server. No information will be released to any person or agency without consent of the subject except as required by law.

Analysis plan for initial questions: To determine whether there is a difference in achieving blood pressure goal by using ABPM or chronotherapy.

Descriptive statistics will be carried out using paired t test (changes in blood pressure from baseline vs after 1 month of change in drug therapy for each patient) and Chi-square test or Fisher's Exact Test (amount of subjects from each group that achieved blood pressure goal).

For researchers other than those named on the protocol, use of the data and samples procured under this study will require approval from the PIs of this study in addition to the IRB.

7. Possible Discomforts and Risks:

Risk to the patient from participation in this study is minimal. Participants will not be subjected to processes beyond what is required for obtaining a satisfactory 24-hour blood pressure evaluation and required for routine monitoring of hypertension. Risks of using the ABPM are none. Slight discomfort may occur while wearing the ABPM device throughout the 24 hours as the device periodically inflates, and there may be modest sleep disturbances at the intervals when blood pressure readings are taken. Aside from

the aforementioned, participants will not have any additional discomforts beyond those associated with routine management of their hypertension.

8. Possible Benefits:

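### The only between-arm test counts everyone at goal at one month as a success and ignores baseline goal status, which could be derived from data already collected

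*Combined protocol and SAP*

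**What the plan says.** Section 5 (Specific Aim) sets the size: "We will enroll 20 participants with uncontrolled hypertension, who are prescribed 3 anti-hypertensive medications", of whom "ten of the patients will be randomized to receive a shift in dosing schedule" and the other ten have therapy modified on their ABPM results.

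The inclusion criterion in section 6 is "Blood pressure of $>130/80$ mmHg". It does not say whether this is an office or ambulatory value, or how recent it must be. Candidates are found through a report from the electronic record.

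The data-collection paragraph of section 6 lists one goal variable, a yes/no item: "whether or not patient was at blood pressure goal at the follow-up visit at one month". No baseline counterpart is listed. The same paragraph does collect "the blood pressure readings from the ambulatory blood pressure monitor at baseline and one month post initiation of change in drug therapy", and the Abstract mentions "office blood pressure values prior to study and one month after modification in therapy".

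The analysis plan in section 6 asks whether the two strategies differ in reaching goal, and tests the "amount of subjects from each group that achieved blood pressure goal" by Chi-square or Fisher's exact test. The other named test is a paired t test of each patient's change, which does not compare the arms. No numeric goal or measurement source is attached to the endpoint.

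**The concern.** To achieve goal should mean to move from above it to at or below it. As written, a patient who was at goal before any change of therapy and is still there at one month counts as a success.

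The protocol gives a reason to think this can happen. Section 4 (Background) says "ABPM is primarily used to diagnose white coat hypertension", and it warns that resistant hypertension can be diagnosed falsely when night-time readings are not available. A patient who qualifies on one reading may therefore be at goal on the baseline ABPM. Section 4 also mentions both 130/80 and 140/90 mmHg, so the unstated goal could be looser than the entry threshold.

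At stake are the attainment rates that the pilot will report, and the sensitivity of its only between-arm test. Both bear on its stated purpose of judging whether ABPM is worth adopting.

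**Working it through.** **Inputs from the documents.** 20 patients, 10 per arm (section 5). The plan gives no alpha, power, effect size or goal rate, so it has no figure to reproduce.

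**Assumptions.** Two-sided alpha 0.05. *w* is the share at goal at baseline on the outcome measure, taken as 0, 20%, 30% or 40%. *r* is the conversion rate among patients above goal at baseline. Patients who start at goal stay there, except in step 4.

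**Step 1, reported attainment.** The rate is w + (1 − w)r. For r = 30%:
- w = 20%: 0.2 + 0.8 × 0.3 = 44%
- w = 30%: 0.3 + 0.7 × 0.3 = 51%
- w = 40%: 0.4 + 0.6 × 0.3 = 58%

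**Step 2, arm difference.** It shrinks to (1 − w)(r₂ − r₁). A true difference of 60 points becomes 48, 42 or 36; one of 40 points becomes 32, 28 or 24.

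**Step 3, power.** *Planned test:* sum the binomial probabilities of all 10 v 10 tables with Fisher p ≤ 0.05, using the step 1 rates. *Test stratified by baseline goal status:* if everyone at goal stays there, that stratum contains only successes and carries no information. The test then reduces to Fisher's test among patients above goal at baseline. Power is averaged over the number of such patients per arm, taken as Binomial(10, 1 − w).

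| w | Planned rates, 20% v 80% | Power, planned | Power, stratified | Planned rates, 20% v 60% | Power, planned | Power, stratified |
|---|---|---|---|---|---|---|
| 0 | 20 v 80 | 64% | 64% | 20 v 60 | 25% | 25% |
| 20% | 36 v 84 | 40% | 60% | 36 v 68 | 14% | 27% |
| 30% | 44 v 86 | 30% | 51% | 44 v 72 | 11% | 21% |
| 40% | 52 v 88 | 22% | 41% | 52 v 76 | 8% | 16% |

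The 27% exceeds the 25% only because Fisher's test is coarse and very conservative at exactly 10 v 10.

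**Step 4, sensitivity.**
- *Fixed totals.* If exactly 4, 6 or 8 of the 20 start at goal and are split at random between the arms, stratified power is 61%, 47% or 34% for 20% v 80%, and 26%, 18% or 13% for 20% v 60%.
- *Imperfect retention.* If only 70% of those at goal stay there, the reported rate for r = 30% is 0.7w + 0.3(1 − w) = 38%, 42% or 46%. For 20% v 80%, enumerating an exact test on the total successes in one arm, conditional on the margins of each stratum, gives power of 50%, 38% or 27%. The planned test has 38%, 28% or 19%. The gain is smaller but remains.

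**Step 5, type I error.** With equal true rates, the actual size of Fisher's test at 10 v 10 is about 0.008 to 0.013 for common rates from 20% to 58%. Patients already at goal do not push it above 0.05.

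**The case against.** The strongest objection is that there may be few such patients, or none. Entry is above 130/80 mmHg, and the only figure that section 4 calls a goal is also 130/80. The Abstract collects office values before and after, section 6 says clinical data come from the clinic's standard equipment, and the goal item is listed apart from the ABPM readings. If goal is office 130/80 and entry rests on a current office reading, w is close to zero. This stands as a condition on the point. It does not remove it, because the documents fix neither the source nor the cut-off of goal, nor the date of the entry reading.

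Second, the proportion at goal at one month among all randomised patients is a legitimate and unbiased comparison of the arms. This also stands. Making the main analysis a comparison of patients above goal at baseline would change the question and hide any loss of goal.

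Third, this is a pilot, and 20 patients limit it more than this choice does. True: for 20% v 60%, power is 25% even if nobody starts at goal.

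A reader might also infer more than the text supports:
- *That some patients will certainly be at goal at baseline, whatever definition is chosen.* The documents give no frequency, and the office 130/80 reading contradicts it.
- *That the baseline information is lost.* It is collected; only the endpoint definition and the analysis leave it out.
- *That one arm is favoured.* In expectation the inflation is the same at a given conversion rate, and randomisation balances *w*. Chance imbalance is possible, but its size is easily overstated. With 4, 6 or 8 such patients the arms differ by at least 2 with probability 58%, 63% or 65%, because an even total allows only even differences. With 5, 7 or 9 it is 30%, 35% or 37%.

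**Conclusion.** The point holds conditionally. The plan counts a patient as having achieved goal without asking whether that patient began above it, and this count is the only between-arm test. If a share of patients start at goal on the outcome measure, attainment is overstated in both arms and the difference shrinks by the factor 1 − w. At an assumed 30% who start and stay at goal, a 30% conversion rate reads as 51%, and power for 20% v 80% roughly halves, from 64% to 30%; stratification brings it back to about 51%. These sizes rest on assumed values of *w*, *r* and retention, and are close to nil under the office 130/80 reading with a current entry value.

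The consequence is lost power and misleading rates, not a false-positive risk. Using baseline status does not make the sample adequate. The change is still worth making: it needs no new data and loses nothing if nobody starts at goal.

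**What to change.** In section 6, data collection: state the source and cut-off of goal, and derive goal status at baseline with the same source and cut-off as at one month, from the readings already collected.

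In section 6, analysis plan:
- Keep all 20 randomised patients in the between-arm comparison, and use an exact test stratified by baseline goal status.
- Report by arm the counts newly at goal, staying at goal and losing goal, alongside the number at goal at baseline.
- Give the comparison restricted to patients above goal at baseline as a supporting analysis. Baseline status precedes the change of therapy, so the restriction introduces no selection by treatment.

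Cost: a few sentences and one derived variable. Downside: the gain in power is smaller if patients at goal at baseline do not all stay there.
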